5.1 Primary endpoint

• Changes in Dermatology Life Quality Index (DLQI) at 12 weeks

DLQI is the sum of 10 sub items, each ranging from 0 to 3. Minimum and maximium of DLQI is 0 and 30 respectively.

5.2 Secondary endpoints

- Change in DLQI at 4 and 24 weeks
- Change in Patient's Global Assessment of Skin Pain (NRS) at 4, 12 and 24 weeks.

NRS consists of two Visual Analogue Scale response questions :

Patient's response on each question can range from 0 to 10

• Change in items of EuroQol (EQ-5D) at 4, 12 and 24 weeks

EQ-5D consists of 5 sub-items:

Mobility Self-care Usual Activities Pain/Discomfort Anxiety/Depression

each classified into levels 1 to 3 where 3 is most severe.

• Change in EuroQol (EQ-5D) VAS score at 4, 12 and 24 weeks

• Change in items of Hidradenitis Suppurativa Impact Assessment (HSIA) at 4, 12 and 24 weeks.

HSIA consist of 18 sub items of which 16 range from 0 to 10 and 2 items register time at work/school and time away from work/school because of HS.

• Change in Work Productivity and Activity Impairment Questionnaire: Specific Health Problem (WPAI:SHP) at 4, 12 and 24 weeks

The WPAI consists of six questions regarding productivity and impairment: (Q1) Currently employed

- (Q2) Hours missed due to specified problem
- (Q3) Hours missed for other reasons
- (Q4) Hours actually worked
- (Q5) Degree problem affected productivity while working
- (Q6) Degree problem affected regular activities

From above questions, four scores will be calculated: Percent work time missed due to problem: [Q2/(Q2+Q4)]*100Percent impairment while working due to problems: (Q5/10)*100Percent overall work impairment due to problem: $\{Q2/(Q2+Q4) + [(1-(Q2/(Q2+Q4)))*(Q5/10)]\}*100$ Percent impairment while doing regular activities: (Q6/10)*100

• Hidradenitis Suppurativa Clinical Response (HiSCR) at 4, 12 and 24 weeks

HiSCR is a clinical endpoint focusing on assessment of HS inflammatory signs and symptoms that will determine the clinical effectiveness of Adalimumab. HiSCR requires:

- At least a 50% reduction in the total abscess and inflammatory nodule count (AN count) relative to baseline, and
- No increase in abscess count, and
- No increase in draining fistula count.

In first bullet AN count is defined as sum of abcess count and inflammatory nodules count.

5.3 Safety endpoints

• Non-serious Adverse events

As the safety profile of Adalimumab is stable and well established, non-serious events will not be actively solicited as these events are not likely to further contribute

to the understanding of the safety profile of the product. Any non-serious reports will be collected as spontaneous reports if notified to AbbVie.

• Serious Adverse events

Serious adverse events will be reported to AbbVie from the time the physician obtains the patient's authorization to use and disclose information (or the patient's informed consent) until 30 days or 5 half-lives following the intake of the last dose of physician-prescribed treatment.

In the CRF the response to the following question is registered at 4, 12 and 24 week visits:

Has any SAE(s) occurred since last visit?

6 Analysis Methods

The final statistical analyses will be performed at Scandinavian Development Services AB, Danderyd, Sweden by using the SAS ® version 9.3 or higher.

Continuous variables will be summarized using descriptive statistics (n, mean, SD, min, median, max). Categorical variables will be summarized in frequency tables (frequency and proportion). Graphical presentations, e.g. describing the change over time, will be used as appropriate, and individual patient data will be listed.

The primary and secondary endpoints (change in DLQI, Patient's Global Assessment of Skin Pain (NRS), EQ-5D VAS score and WPAI:SHP at 4, 12 and 24 weeks) will be analyzed using paired samples t-tests or non-parametric methods such as Wilcoxon signed rank test as appropriate.

HiSCR is a dichotomous response variable which will be analysed descriptively presenting proportion HiSCR with binomial exact 95% confidence interval.

The change at 12 weeks will be of primary interest.

Visit windows regarding 4, 12 and 24 weeks assessments following first dose of Adalimumab will decide the validity of assessment.

•	Baseline	Last assessment before first dose of Adalimumab
•	4 weeks	Day $(4*7)$ - $(3*7) \ll 4$ weeks \ll Day $(4*7)$ + $(3*7)$

•	12 weeks	Day (12*7)-(4*7)	<= 12 weeks <= Day (12*7)+(4*7)
•	24 weeks	Day (24*7)-(7*7)	<= 24 weeks <= Day (24*7)+(7*7)

Assessments outside these visit windows will not be part of input for summaries by visit. Such assessments will only be presented in listings.

When multiple assessments are found inside the same visit window the assessment most close to the planned visit day (day 28, 84 or 168) will be selected. In case two assessments are equally close to the planned visit day, one X days before and the other X days after planned day, the later of the assessments will be selected. The assessments which was not selected will only be presented in listings.

No adjustment for multiple comparisons will be made.

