3.2 Number of patients

3.2.1 Sample size calculations

With 50 evaluable patients, the power is 90% based on a change in DLQI of -5.4, and an assumed standard deviation of 11.5 and type I error of 5% (two-sided). The dropout rate is considered to be low, approximately 5% after 12 weeks, which will have a minimal impact on the power (decreased to 88%).

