4.3 Effectiveness analysis sets

4.3.1 Full analysis Set (FAS), (modified Intention-to-treat(ITT)

The FAS will include all enrolled patients, with the exception of subjects who were enrolled and not treated with any dose of adalimumab, or who had no baseline or post baseline data collected for the primary endpoint Dermatology Life Quality Index (DLQI). In case all of a patients post baseline assessments of DLQI are outside visit windows, the patient is excluded from FAS.

The FAS will be used for baseline characteristics and analysis of effectiveness.

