4.3.2 Per protocol analysis set (PP)

Criteria for the determination of the PP population will be finalized prior to database lock, and will include the following:

- Study subjects included in FAS
- Study subjects meeting all inclusion criteria and none of the exclusion criteria
- Study subjects with a valid 12 week assessment(according to visit windows) for the primary endpoint Dermatology Life Quality Index
- Study subjects who up until the valid 12 week assessment have less than 4 missed doses of Adalimumab

The PP analysis set will be used as sensitivity analysis for the primary effectiveness endpoint.

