6.2.1 Missing data

In general imputation of missing observations will not be performed. Missing data will be reported descriptively.

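### Counted in days, the SAP visit windows leave days 50–55 and 113–118 in no visit, so a DLQI taken 29–34 days after day 84 is listed but lost to the primary analysis (minor, cheap to improve)

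*SAP*

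**What the plan says.** SAP section 6 (Analysis Methods) counts visits from the first dose of adalimumab. It allows 3 weeks either side of week 4, 4 weeks either side of week 12 and 7 weeks either side of week 24. The upper limits of the last two windows read "<= 12 weeks <= Day (12*7)+(4*7" and "<= 24 weeks <= Day (24*7)+(7*7" (closing brackets omitted).

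The rules that act on these windows are:

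- **Outside a window (section 6):** "Assessments outside these visit windows will not be part of input for summaries by visit". Such values go to listings only.
- **Several values in one window (section 6):** "When multiple assessments are found inside the same visit window the assessment most close to the planned visit day" is used, the planned days being 28, 84 and 168.
- **Full analysis set (section 4.3.1):** "In case all of a patients post baseline assessments of DLQI are outside visit windows, the patient is excluded from FAS".
- **Per-protocol set (section 4.3.2):** one condition is "Study subjects with a valid 12 week assessment(according to visit windows) for the primary endpoint Dermatology Life Quality Index".
- **Missing data (section 6.2.1):** "In general imputation of missing observations will not be performed".

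The primary endpoint is the change in DLQI at 12 weeks (section 5.1). Visits take place in routine care at only approximately 4, 12 and 24 weeks (section 3.1).

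**The concern.** In whole weeks the three windows join without a break: weeks 1–7, 8–16 and 17–31. In days they do not, because each window ends on the exact day of its last week and the next opens seven days later. Six days between each pair of neighbouring windows are assigned to no visit, and the SAP gives no reason.

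The gap that matters for the primary endpoint is days 113–118. A DLQI collected then is closer to the week-12 target than to the week-24 target but counts for neither. Nothing is imputed in its place. The per-protocol analysis requires an in-window week-12 value, so it drops the same patients and cannot act as a check. A patient whose post-baseline DLQIs all fall outside the windows also leaves the full analysis set.

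What is at stake is a small number of primary values that have already been collected, in a study of 50 patients.

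**Working it through.** **1. The plan's own power figure.** Inputs from SAP section 3.2.1: change −5.4, SD 11.5, two-sided 5%, 50 evaluable patients, about 5% dropout at 12 weeks. For a paired t-test the noncentrality is (5.4/11.5)·√n, with n − 1 degrees of freedom. This gives 90.2% at n = 50 (stated: 90%). With dropout, 50 × 0.95 = 47.5; at n = 47 the power is 88.3% (stated: 88%). Both figures are reproduced.

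**2. The windows in days (SAP section 6).**

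- Week 4: 28 ± 21 = days 7–49
- Week 12: 84 ± 28 = days 56–112
- Week 24: 168 ± 49 = days 119–217

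The unassigned days between windows are 50–55 and 113–118. Days 113–118 lie 113 − 84 = 29 to 118 − 84 = 34 days after day 84, and 168 − 113 = 55 to 168 − 118 = 50 days before day 168.

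**3. How many week-12 visits could fall there.** The documents give no spread of visit days. Assumption: normal around day 84, SD 10, 14 or 21 days, with half-day limits.

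| | SD 10 | SD 14 | SD 21 |
|---|---|---|---|
| P(112.5 to 118.5), the late gap | 0.2% | 1.4% | 3.7% |
| Late gap × 50 patients | 0.1 | 0.7 | 1.9 |
| All visits outside days 56–112 | 0.4% | 4.2% | 17.5% |
| All visits outside days 56–118 | 0.3% | 2.8% | 13.8% |

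By symmetry, days 50–55 hold the same share of week-12 visits as days 113–118.

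**4. Effect on power, starting from n = 47 after dropout.** Every out-of-window loss is counted, not only the gap.

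| | SD 10 | SD 14 | SD 21 |
|---|---|---|---|
| n, current windows: 47 × (1 − share outside 56–112) | 46.8, about 47 | 45.0, about 45 | 38.8, about 39 |
| Power | 88.3% | 86.9% | 81.5% |
| n, gap closed: 47 × (1 − share outside 56–118) | 46.9, about 47 | 45.7, about 46 | 40.5, so 40–41 |
| Power | 88.3% | 87.6% | 82.5–83.5% |

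Closing the gap recovers 1.4/4.2, about a third, of the out-of-window loss at SD 14, and 3.7/17.5, about a fifth, at SD 21.

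**5. Side calculations.** With week-4 visits normal around day 28, days 50–55 hold 1.3% at SD 10 or 3.8% at SD 14 (0.6 or 1.9 of 50); these values are lost to secondary analyses. With week-24 visits normal around day 168, days 113–118 hold 0.02% at SD 14 or 0.5% at SD 21 (at most 0.3 of 50).

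**The case against.** The strongest reply is that this is an openly stated design choice. The windows are symmetric, the SAP says that they decide validity, it sends other values to listings, and section 4.3.1 provides for patients with no in-window DLQI. No sentence promises that every day belongs to a visit. This stands: there is no contradiction in the SAP. A reader might infer from the unbroken whole weeks that the gaps are a slip in converting weeks to days. That is plausible, but the documents do not say so.

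A second reply is that any finite window loses late visits and that the gap is the lesser part of that loss. This also stands. At SD 21 most of the fall from 88.3% to 81.5% comes from visits outside days 56–112 that closing the gap would not rescue. It would be wrong to attribute that whole fall to the gap.

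A third reply is that the SAP's closest-day rule chooses among values already inside one window and does not allocate days across windows. That is correct. Giving days 113–118 to week 12 extends the idea; closeness alone would put the cut at the midpoint, (84 + 168)/2 = day 126.

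A reader might also infer that the SAP leaves open whether a visit is placed by its label or by its actual day. The text does not support making a point of this. Section 6 counts from first dose and speaks of assessments found inside a window, which reads naturally as actual-day allocation.

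What survives is narrow: two unexplained six-day gaps that discard values a neighbouring visit could take.

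**Conclusion.** The point holds as a minor one. Days 50–55 and 113–118 belong to no visit, and a DLQI on days 113–118 is lost to the primary analysis and to its only sensitivity analysis. Under the assumed visit-day distributions the primary gap involves about 0.1 to 1.9 of 50 patients. After dropout, closing it adds nothing visible at SD 10, about 0.7 percentage points of power at SD 14 (86.9% to 87.6%) and 1 to 2 points at SD 21 (81.5% to 82.5–83.5%). For scale, the SAP describes its own fall in power from 90% as one "which will have a minimal impact on the power (decreased to 88" percent.

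The sizes rest on a normal distribution and on SDs that no document supplies. A reader might infer that the gaps distort the DLQI estimate. The documents do not support that: nothing links the outcome to falling in a gap, the values remain visible in listings, and missing data are reported descriptively. The reason to act is that the change is cheap and keeps primary data already collected.

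**What to change.** Before final database lock:

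1. Define gap-free windows: week 4 = days 7–55, week 12 = days 56–118, week 24 = days 119–217. Each gap day goes to the nearer planned day.
2. Report the primary result under both the current and the gap-free windows, with a table of actual visit days.
3. If interim data have already been seen, keep the current windows as primary and show the gap-free windows as a sensitivity analysis. This matters because SAP section 6.1.5 provides for interim results to reach investigators and be published.
4. Optionally, add a further sensitivity analysis with the cut between weeks 12 and 24 at the midpoint, day 126.

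Protocol Amendment 1 (section 9.7) ties finalization of the SAP to both the interim and the final lock, so a revision before final lock is feasible. The interim analysis does not use visit windows and is unaffected.

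The cost is a short SAP edit, one small table and one extra run of the primary test. There are three downsides. Week 12 becomes asymmetric (−28/+34 days). Early week-12 visits on days 50–55 go to week 4 and are not recovered for week 12. A week-24 visit held 50–55 days early could count as week 12 (at most about 0.3 of 50 patients at SD 21).

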6.1 Interim analysis

6.1.1 Purpose of the interim analysis

Slow patient recruitment has delayed the study and to provide data according to original plan an interim analysis will be performed in Q2 2017. No formal statistical tests will be performed on the interim data.

No adjustment of final analysis will be made regarding the blinded interim analysis.

6.1.2 Planned Schedule of the interim analysis

NA. Choice of timepoint for Interim analysis is based on administrative reasons.

6.1.3 Scope of adaptations

NA. No actions will be taken based on the descriptive interim analysis.

6.1.4 Methods to minimize bias in the type I error rate

NA. Since this is a Post Marketing Observational Study of one single treatment no method can be applied to minimize bias.

6.1.5 Practical measures to minimize bias

None. Preserving data integrity is not possible since the purpose of the interim analysis is to provide information to investigators and to publish data.

Assignment of personnel to perform the interim analysis

Since purpose of Interim analysis is to provide information to investigators and to publish data the praxis of not allowing SDS personnel to be involved both in interim and final analysis is relaxed.

Limiting access of data and results within SDS

Since purpose of Interim analysis is to provide information to investigators and to publish data the praxis of not allowing access to interim data for SDS personnel involved in final analysis is relaxed. This includes personnel possibly involved in production of protocol amendments, the SAP and data base lock.

Communicating interim results to sponsor

The Baseline characteristics and endpoints listed below will be analyzed descriptively and presented to Sponsor. Continuous Baseline characteristics will be summarized using descriptive statistics (n, mean, SD, min, median, max). Categorical baseline variables will be summarized in frequency tables (frequency and proportion).

Effectiveness endpoints DLQI, NRS, HSIA and HiSCR will be presented in listings.

- Baseline demographics •
 - o Age
 - o Gender
 - Smoking status
 - o BMI
 - Time from first HS symptoms to HS diagnosis \cap Time point for first HS symptom is registered as year of symptom. In calculation of time from first HS symptom to HS diagnosis all symptom starts are assumed to have begun on June 30 except for when symptom starts in year of HS diagnosis. In the latter case symptoms is assumed to have started on January 1.
 - Time from HS diagnosis to start of Humira treatment start.
 - Relevant Medical history(Current and Previous)
 - Proportion Hurley II och III (from HiSCR)
 - WPAI components including WPAI-score
- DLQI components including DLQI-score Patient data (no summary) at BL, week 4 and 12.
- NRS, Patient data (no summary) at BL, week 4 and 12 for •
 - Worst pain during last 7 days
 - Average pain during last 7 days
- HSIA components

Patient data (no summary) at BL, week 4 and 12

• HiSCR responders/ non-responders Patient data (no summary) at BL, week 4 and 12

Interim results will be based on all enrolled patients. Visit windows will not be used in interim analysis.

Documentation and storage

Interim data, scripts and outputs will be stored in a secure folder at SDS server.

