9.3 Variables

9.3.1 Demographic/baseline data

The following data will be collected at the baseline visit:

- Demographic/Baseline data
 - Age, gender and ethnicity
 - Smoking habits
 - Body Mass Index (BMI)
 - Age when HS symptoms started
 - Date of diagnosis
 - HS assessment (lesion count and Hurley stage)

- Adalimumab treatment start (info on missed doses will be collected at 4, 12 and 24 weeks)
- Previous treatment(s) for HS
- Previous surgery for HS (info on new surgeries for HS will be collected at 4, 12 and 24 weeks)
- Co-morbidities
- Concomitant medications (changes in Concomitant Medication will be collected at 4, 12 and 24 weeks)

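### When onset and diagnosis share a year, the SAP's symptom-onset rule gives the longest possible diagnostic delay, although it uses mid-year in all other cases

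*SAP*

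**What the plan says.** SAP 6.1.5 lists time from first HS symptom to HS diagnosis among the baseline characteristics for the interim. On the precision of onset it states: "Time point for first HS symptom is registered as year of symptom". It then sets the date: "all symptom starts are assumed to have begun on June 30 except for when symptom starts in year of HS diagnosis". For the exception it adds: "In the latter case symptoms is assumed to have started on January 1".

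The variable is reported by summary statistics: "Continuous Baseline characteristics will be summarized using descriptive statistics (n, mean, SD, min, median, max"). The same section says that the interim is meant to inform investigators and to publish data.

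Protocol 9.3.1 collects the other end of the interval, "Date of diagnosis". It names the onset item as "Age when HS symptoms started", whereas the SAP works from a year; how one becomes the other is not described.

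The SAP gives no reason for January 1, no sensitivity check and no expected share of same-year patients.

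**The concern.** The two halves of the rule follow different principles. When the years differ, the rule takes the middle of the interval in which onset could lie. When they coincide, it takes the far end of that interval. The first choice errs in both directions and roughly cancels; the second can err in only one.

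The rule also ranks patients oddly. Take onset in 2014 with diagnosis on 1 January 2015: the true delay lies between 1 and 365 days, and the rule scores 185 days. Take onset in 2015 with diagnosis on 31 December 2015: the true delay lies between 0 and 364 days, and the rule scores 364. Two patients with nearly the same range of possible delays get values that differ by about a factor of two.

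At stake is the accuracy of one published descriptive figure, the diagnostic delay in Swedish HS patients. Protocol 7.3 gives support for reimbursement as one reason for collecting national data, so an avoidable one-way bias is worth removing even if it is small.

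**Working it through.** The documents state no figure for diagnostic delay, so there is nothing to reproduce first.

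**Inputs from the documents.** Onset is known to the calendar year; the imputed date is June 30 or January 1 (SAP 6.1.5); diagnosis date is collected (Protocol 9.3.1). I assume the diagnosis date is complete, since the SAP does not say how a partial one is handled.

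**Same-year group.** Let *d* be the days from January 1 to diagnosis.

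- SAP rule: delay = *d*.
- Onset uniform on the interval from January 1 to diagnosis: expected delay = *d* − *d*/2 = *d*/2.
- Ratio = *d* / (*d*/2) = 2 for any *d*. The excess is *d*/2, at most about 6 months.

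| *d* (days) | SAP rule | Midpoint | June 30, if there were no exception |
|---|---|---|---|
| 91 | 91 | 45.5 | −90 |
| 182 | 182 | 91 | 1 |
| 365 | 365 | 182.5 | 184 |

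The last column shows why some exception is needed. The midpoint column shows that negative delays can be avoided without January 1.

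Simulated group means (3,000,000 draws): 6.0 months under the rule against 3.0 true if diagnosis dates are uniform over the year and onset is uniform before them; 8.0 against 4.0 if both dates are uniform with onset first.

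**Sensitivity of the factor.** If onset lies on average a fraction *f* of the way from January 1 to diagnosis, the ratio is 1/(1 − *f*): 1.5 at *f* = 1/3, 2 at 1/2, 3 at 2/3. It equals 1 only at *f* = 0, when onset really was January 1. With exponential delays of mean 1 to 10 years it runs from 2.27 down to 2.02.

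**Effect on the overall mean.** Replacing the midpoint by January 1 raises the overall mean by (same-year share) × (mean *d*)/2. The shares and mean *d* below come from an assumed uniform onset within the year and exponential delay.

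| Assumed true mean (yr) | Same-year share | Mean *d* (months) | Added by January 1 | Median, SAP rule / midpoint (yr) |
|---|---|---|---|---|
| 1 | 0.368 | 7.69 | 0.368 × 7.69/2 = 1.41 months = 0.12 yr | 0.89 / 0.74 |
| 2 | 0.213 | 7.84 | 0.213 × 7.84/2 = 0.83 months = 0.07 yr | 1.41 / 1.41 |
| 5 | 0.094 | 7.93 | 0.094 × 7.93/2 = 0.37 months = 0.03 yr | 3.49 / 3.49 |
| 7 | 0.068 | 7.94 | 0.068 × 7.94/2 = 0.27 months = 0.02 yr | 4.86 / 4.86 |

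The median is unchanged once it exceeds one year, because same-year patients score at most about one year under either rule.

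**What January 1 does not explain.** The total excess of the SAP rule over the true mean is about 0.19, 0.11, 0.05 and 0.04 year at means of 1, 2, 5 and 7 years. With the midpoint it falls to 0.07, 0.04, 0.02 and 0.02. That remainder comes mostly from the June 30 convention when delays are short. When delays are long, June 30 is nearly unbiased: at a mean of 7 years the different-year group averages 90.1 months under the rule against 89.8 true.

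**The case against.** The strongest objection is that the point is immaterial. It concerns one descriptive baseline variable. The interim carries no formal tests, and SAP 6.1.3 says that no action will follow from it. If delays run to many years, the mean shifts by a few hundredths of a year and the median not at all. All of this stands, and it limits the point to a minor refinement.

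A second objection is that an exception is unavoidable and that January 1 is explicit, prespecified and can never give a negative delay. That is true, but the midpoint has the same three properties and no built-in upward error. The need for an exception therefore does not justify this one.

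A reader might also infer more than the documents support:

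- *That the rule doubles the delay outright.* Exact doubling needs uniform onset between January 1 and diagnosis. This extends the SAP's own mid-interval convention, but it is not stated anywhere, and in a chronic, recurrent disease onset may not be spread evenly over that interval.
- *That mid-year applies to most patients.* No same-year share is given, so this cannot be checked.
- *That January 1 accounts for all of the overstatement.* Part of it comes from June 30, as shown above.
- *That the final analysis is affected too.* The rule appears only in the interim section. The demographics listed in SAP 6.3.3 do not include diagnostic delay, and SAP 6.3 mentions disease characteristics without naming it.

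**Conclusion.** The point holds as a small, one-directional bias in a single descriptive variable. That January 1 gives every same-year patient the maximum possible delay follows from the SAP text alone. The factor of 2 in that group is conditional on uniform onset; other assumptions give other factors, all above 1 unless onset was January 1.

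The effect on the overall mean rests on assumed exponential delays, because the documents supply no distribution. On that basis the January 1 choice adds between about 0.02 year (mean delay 7 years) and 0.12 year (mean delay 1 year), and it moves the median only in the 1-year case. No endpoint, analysis set, test or power figure depends on it. The correction is worth making because it is nearly free and the figure is intended for publication.

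**What to change.** Replace the last sentence of the rule in SAP 6.1.5 with wording such as: *When the onset year equals the diagnosis year, onset is taken as the midpoint between January 1 of that year and the date of HS diagnosis.* Use the same rule in the final analysis only if this variable is reported there.

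The cost is one sentence and one line of code, and no new data are needed because the diagnosis date is already collected. If the sponsor prefers to keep January 1, the SAP should give the reason, and the report should state how many patients fall in the same-year group so that readers can judge the effect.
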